5.4 Treatment Delivery

The population that is eligible for this study would not be eligible for RSBY under the program's usual rules. To make this study possible, we exchanged letters of cooperation with the state in which we conducted the study (Karnataka), the central government agency (Ministry of Labor) responsible for administration of RSBY, and the development organization (GIZ) providing technical support for RSBY.

Sample households were randomized in August 2014 using data from the listing exercise. They were informed of their treatment assignment and, depending on which arm to which they are assigned, given access to insurance or cash in May and June 2015. This step took place roughly 18 months after the baseline due to government constraints. Due to challenges associated with evaluating a government program, we were only able to enroll sample households when the government held its RSBY enrollment drive in early 2015.

We enrolled study households much in the same way the government enrolled RSBY (non-study) eligible households into the program: via a mobile enrollment truck that visited each village. One difference is that we went to each household to ask them if they would like to enroll and took them to the enrollment truck, which was parked in one place in the village. By contrast, the government informed non-study households by delivering paper notices (chits) to each home about when and where the enrollment truck would be in the village.

Roughly 78.4%, 70.4% and 58.6% of households in arms A, B, and C, respectively enrolled in RSBY. Enrollment rates are somewhat higher in Gulbarga than Mysore: 77.9/76.4/64.1% v. 78.8/63.5/52.3% in A/B/C. No one in arm D enrolled.

For all study households that take up insurance, we paid the government their premiums. For households in arms A, this was funded by grant funds. For those in B and C that purchase insurance, this was funded by the respondents' money.

The Karnataka government renewed RSBY automatically for non-study and study households in 2016 and 2017 without any action—even payment—by enrollees. RSBY ended in the state on August 31, 2018, to make way for the new NHPS scheme, which is scheduled to start in late 2018 or early 2019. As of this writing, Karnataka had agreed to roll out NHPS but had not begun the roll-out.

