10.1 Higher price causes greater utilization

We test whether the midline finding persists at endline in two ways:

- We examine whether group C households have higher rates of attempts to use RSBY and successful efforts to use RSBY.
- Because households with more members have a lower effective price per member¹⁸, larger households should have greater utilization per capita (as opposed to per household).

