10.2 Selection

We test this explanation by testing its assumptions or predictions:

- Individuals who were differentially sick or risk averse at baseline are more likely to enroll in RSBY in the first place and/or retain the RSBY card at midline and endline, conditional on household group assignment.
- Total utilization should be weakly higher in household group A than C. Equivalently, average utilization including both enrollees and non-enrollees, i.e., the ITT estimates of utilization, should be higher in A.¹⁹
- After predicting those in group A likely to enroll if they were in group C, we test to see if they have higher utilization conditional on getting insurance.

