10.3 Price signaling

We test this explanation by testing its prediction that, assuming individuals learn about prices not just from their own experience but also from the experience of their peers, individuals who live in villages where there are more people who received insurance at a lower price (e.g., zero) should perceive insurance as having less value and thus purchase it less themselves. We test this prediction by examining the following:

- Holding constant the group assignment of a household, the household should attempt to or utilize care more the higher is price paid by other households that are both in the study sample and in the same village.

¹⁸The price of RSBY is fixed under our study—and for BPL families in the actual scheme—regardless of the size of the household.

¹⁹By contrast, average utilization could be lower in A than C if you only look at enrollees, i.e., the CATE estimates for A could be lower than for C even if there is selection.

- Holding constant the group assignment of a household, the household should attempt to or utilize care more the higher the price paid by other households that are in the same village, including both other households in the village and the fraction of households in the village that are below the poverty line.

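### Higher ITT card use in A than in C (Section 10.2) does not support selection: A's higher enrolment rate (ratio 1.34) produces it with no selection, so only a clear failure is informative

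*Combined protocol and SAP*

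**What the plan says.** Section 10 sets out to explain a midline result: use of the RSBY card was higher in C, the arm that paid the premium and received no cash. It names three candidate explanations: selection, price signaling and sunk costs.

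- Section 10.1 repeats the comparison at endline: "We examine whether group C households have higher rates of attempts to use RSBY and successful efforts to use RSBY". It does not say whether the rates are per assigned or per enrolled household.
- Section 10.2 tests selection with three bullets. The first relates baseline sickness and risk aversion to enrolling or keeping the card. The second is "Total utilization should be weakly higher in household group A than C", restated as "average utilization including both enrollees and non-enrollees, i.e., the ITT estimates of utilization, should be higher in A". The third reads "After predicting those in group A likely to enroll if they were in group C, we test to see if they have higher utilization conditional"; the condition is that they hold insurance.
- Footnote 19, attached to the second bullet, adds that among enrollees alone "the CATE estimates for A could be lower than for C even if there is selection".
- Section 10.4 offers no test of its own. It counts failure to support selection and signaling as evidence for sunk costs.

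The enrolment figures are in Section 5.4: "Roughly 78.4%, 70.4% and 58.6% of households in arms A, B, and C, respectively enrolled in RSBY". By district: "Enrollment rates are somewhat higher in Gulbarga than Mysore: 77.9/76.4/64.1% v. 78.8/63.5/52.3% in A/B/C".

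**The concern.** Use per assigned household is the product of two things: the share of households holding a card, and use per card holder. Free RSBY put cards in more A households than C households, so the product can favour A whatever the reason C enrollees use their cards more. A prediction supports an explanation only if it would be unlikely to hold without that explanation, and here it is expected without it.

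At stake is part of evaluation question 2 (whether prices affect utilization, and how). Section 10.4 works by elimination, so it matters what counts as support for selection, and errors are possible in both directions. A near-automatic pass can credit selection where there is none. A failure can be read as no selection, and so as sunk costs, when selection is real but accompanied by a modest price effect.

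The unstated denominator in 10.1 adds to this. If it is per assigned household, a positive card-use finding against A is the second bullet's contrast with the sign reversed. If it is per enrollee, C enrollees chose to pay, and the causal language of the 10.1 heading does not follow.

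**Working it through.** **Inputs.** Enrolment in A and C, overall and by district (Section 5.4); target arm sizes 4,500 and 2,250 (Section 5.2); 10% attrition allowance (Section 5.1). The documents give no size for the midline finding and no card-use rate.

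**Consistency of the enrolment rates.** The district weights are not stated. A Gulbarga weight of 0.535 gives:
- A: 0.535 × 77.9 + 0.465 × 78.8 = 78.3
- B: 0.535 × 76.4 + 0.465 × 63.5 = 70.4
- C: 0.535 × 64.1 + 0.465 × 52.3 = 58.6

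All are within 0.1 point of the pooled figures, so the rates agree with each other.

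**1. Card use, no selection.** Let u be use per A enrollee and r the price effect per enrollee in C. Then A/C per assigned household = 0.784u / (0.586ru) = 1.338/r.

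| r | A/C | Prediction |
|---|---|---|
| 1.0 | 1.338 | holds |
| 1.1 | 1.216 | holds |
| 1.2 | 1.115 | holds |
| 1.3 | 1.029 | holds |
| 1.4 | 0.956 | fails |
| 1.5 | 0.892 | fails |

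The break-even is r = 78.4/58.6 = 1.338 overall, 77.9/64.1 = 1.215 in Gulbarga and 78.8/52.3 = 1.507 in Mysore. With no selection in either district, a 40% price effect passes in Mysore (0.523 × 1.4 = 0.732 against 0.788) and fails in Gulbarga (0.641 × 1.4 = 0.897 against 0.779).

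**2. Card use, pure selection.** Suppose everyone who would enrol under C would also enrol under A. The extra 78.4 - 58.6 = 19.8% of households then use s times as much as C enrollees, with s between 0 and 1. A/C per assigned household = (0.586 + 0.198s)/0.586. Use per enrollee, C to A, = 0.784/(0.586 + 0.198s).

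| s | A/C per assigned household | C/A per enrollee |
|---|---|---|
| 1 (no selection) | 1.338 | 1.000 |
| 0.5 | 1.169 | 1.145 |
| 0 (strongest) | 1.000 | 1.338 |

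The margin in favour of A is widest with no selection and shrinks to nothing as selection strengthens. For any per-enrollee ratio from 1 to 1.338, pure selection and a pure price effect give the same ITT result. Above 1.338 pure selection is impossible, and the check fails as it should.

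**3. Both at once.** With s = 0 and r = 1.1, A/C = 0.586/(0.586 × 1.1) = 0.909. The check fails although selection is at its strongest.

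**4. General utilization.** Hospital visits, nights and day surgeries (Section 8.2) also occur without a card. If non-enrollees use k times what A enrollees use, A = 0.784u + 0.216ku and C = 0.586ru + 0.414ku. Break-even r = (0.784 - 0.198k)/0.586 = 1.338 - 0.338k: 1.34 at k = 0, 1.17 at k = 0.5, 1.00 at k = 1. A 30% price effect passes at k = 0 (0.784u against 0.762u) but fails at k = 0.5 (0.892u against 0.969u).

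**5. Sampling error (illustration; card-use rate and design effect are assumed).** Take 4,050 and 2,025 households (targets less 10%), no selection, and a normal approximation with design effect 1 to 2. The probability that the estimate has A at or above C is:

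| Card use per A enrollee | r = 1 | r = 1.2 | r = 1.5 |
|---|---|---|---|
| 5% | 0.98 to 0.93 | 0.79 to 0.71 | 0.19 to 0.27 |
| 10% | 0.998 to 0.98 | 0.87 to 0.79 | 0.11 to 0.19 |
| 20% | above 0.99 | 0.95 to 0.88 | 0.03 to 0.09 |

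Requiring significance does not cure this. At 10% use and r = 1, A is significantly above C with probability 0.84 to 0.55, with no selection present.

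**6. Total against average.** The plan treats the two as equivalent. At the target sizes, A would enrol 4,500 × 0.784 = 3,528 households and C 2,250 × 0.586 = 1,318.5, a ratio of 2.68, so literal totals would favour A still more.

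**The case against.** The strongest defence is that the second bullet is a legitimate one-way test: it states what selection predicts, and if C clearly exceeds A, pure selection is refuted. That stands. A reader might infer that the check cannot separate selection from a price effect at all. The arithmetic from the documents' own enrolment rates does not support this, because a large enough price effect makes it fail. For the same reason, opposite predictions in 10.1 and 10.2 are not a fault in themselves.

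Second, a reader might infer that evaluation question 2 hangs on this check. It does not. Bullets 1 and 3, Section 10.3, and the Section 7.3 hypothesis on price-elasticity of take-up by predicted inpatient use all bear on it. Bullet 3 looks at A households, all at zero price, so a difference there cannot be an own-price or sunk-cost effect. It can show that selection exists. As worded, though, it includes no comparison with C enrollees, so it does not show how much of the gap selection accounts for. The plan promises only to judge which explanations have merit, so a decomposition improves on the plan rather than repairing a broken promise.

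Third, the 1.34 figure needs non-enrollees to have no use. This is correct, and it confines that figure to card use.

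Fourth, footnote 19 already separates the all-household from the enrollee-only comparison. It does, but it warns only that the enrollee comparison may reverse. It does not say that the all-household comparison passes without selection.

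Fifth, restating 10.1 per enrollee alone would give up a randomized contrast. That also stands, and both denominators should be reported.

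**Conclusion.** The point holds in limited form. A pass on the second bullet is not evidence for selection, and only a clear failure is informative. What a failure refutes is selection as the sole explanation, not selection as such. For card use, the prediction holds in expectation with no selection for any price effect up to about 34% per enrollee (22% in Gulbarga, 51% in Mysore). For general utilization the room is smaller and depends on k, which the documents do not give.

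The card-use result assumes that non-enrollees have no card use. The reading of a failure also assumes that households enrolling at a price would enrol when free. Spillovers are left out of the arithmetic.

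Two further inferences should be avoided. The 34% is a difference in enrolment rate, not in number of households: allocation is 2:1, so the counts differ by more. Nor can it be said that the trial's data fall in the uninformative range, because the midline finding is reported without size or denominator.

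The main ITT estimates are not affected. What is affected is the attribution of the price finding under Section 10.4.

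**What to change.** 1. In 10.2, state that the A-against-C check can only refute pure selection and that passing it is not support. Rest support for selection on bullets 1 and 3 and the Section 7.3 adverse-selection hypothesis. Replace the total with the per-household average, and choose between the weak and strict inequality.
2. Extend bullet 3. Fit enrolment models on baseline variables separately in A and C, and weight each A enrollee by the predicted probability of enrolling under C divided by that under A. Compare their card use with that of C enrollees. Report the part of the gap that the weighting removes as selection on observed variables, and the rest as price effect plus any unobserved selection.
3. In 10.1, report the card-use contrast per assigned and per enrolled household, and do not describe the per-enrollee contrast as causal.

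This costs some wording and one extra weighted analysis. It uses data already collected or planned and builds on the enrolment prediction that bullet 3 already needs. The downside is a more cautious conclusion on selection, since the remainder in step 2 does not fully separate price from unobserved selection.

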10.3 Price signaling

We test this explanation by testing its prediction that, assuming individuals learn about prices not just from their own experience but also from the experience of their peers, individuals who live in villages where there are more people who received insurance at a lower price (e.g., zero) should perceive insurance as having less value and thus purchase it less themselves. We test this prediction by examining the following:

- Holding constant the group assignment of a household, the household should attempt to or utilize care more the higher is price paid by other households that are both in the study sample and in the same village.

¹⁸The price of RSBY is fixed under our study—and for BPL families in the actual scheme—regardless of the size of the household.

¹⁹By contrast, average utilization could be lower in A than C if you only look at enrollees, i.e., the CATE estimates for A could be lower than for C even if there is selection.

- Holding constant the group assignment of a household, the household should attempt to or utilize care more the higher the price paid by other households that are in the same village, including both other households in the village and the fraction of households in the village that are below the poverty line.

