First, we measure ITT effects accounting for spillovers at the village level by examining the predicted effects on outcomes for a household in a given group at different shares of the village sample in that group. The specific shares selected could be in-sample shares or out-of-sample shares. We will highlight when we make out-of-sample predictions.¹² In cases where we want to report ITT under sample average spillovers, we will exclude interaction between household arms and, e.g., village arms.

Second, we make assumptions required for unbiased estimation of, (γ_h, λ_{hv}) with spillovers as given in [name], Jiang, and [name] (2019). The key assumption is partial non-interference, i.e., assignments in villages $j' \neq j$ do not influence outcomes in another village j .

Third, to test for the existence of spillover effects, we conduct the Wald test with the null hypothesis that $\beta_v = \beta_{v'}$ and $\lambda_{vh} = \lambda_{v'h}$ for any $v \neq v'$ and $h = 1, 2, 3, 4$. This test can be conducted for both take-up and any outcome variable of interest.

¹⁰<https://imai.fas.harvard.edu/research/files/spillover.pdf>.

¹¹Berry et al. (2018) consider different subsidies and associated extrapolation issues.

¹²Although our study varies the fraction of subjects in a village who receive access to insurance in some form, we do not – as Table 1 shows – give some treatment to no households or some treatment to all households. Therefore, to estimate the above parameter of interest we have to make out-of-sample predictions.

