11. Age or child/adult status
12. Marital status, birth order and relationship to household head
13. Size of village
14. Percent of village assigned to access to RSBY via this RCT
15. Percent of village eligible for RSBY outside the RCT
16. Hospital utilization in prior year (measured at baseline) or predicted hospitalization
17. Health status or serious sickness
18. Cognitive capacity
19. Willingness to pay for insurance (predicted based on data from a randomly selected sample of households removed from main RCT and chosen to participate in a WTP study)
20. Risk and time preferences
21. Assets and savings
22. Urban, peri-urban, and rural status
23. Monthly expenditure budget
24. Experiencing a serious health shock in the past year (provided this is balanced across treatment arms)

Predicting utilization. A natural dimension along which the impact of insurance may differ is the latent propensity of a household to experience health shocks which would require inpatient care. Since this variable is latent, it must be estimated. We will machine learning methods to predict households' likelihood to experience an inpatient hospitalization. We will perform this exercise on two samples: the baseline data (across all treatment arms) and the post-intervention data (using only group D, the control group). The resulting model will then be used to generate predictions for the full sample. Our key hypotheses are (1) that the impact of the offer of insurance will lead to larger treatment effects for those with higher propensity; and (2) that demand for insurance will be less price-elastic among those with higher propensity (i.e., adverse selection). Hypothesis (2) will be tested by examining how takeup of insurance varies between free and not free (group A vs. groups B and C) for high- vs. low-propensity households.

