8.1 Demand for insurance

8.1.1 Uptake

- Take up RSBY at enrollment (in 2015)

¹⁴We will also consider multiple testing approaches as raised in Lee and Shaikh (2014).

- Possession of RSBY card at endline
- Possession of RSBY card in past
- No longer have RSBY card
- Number of household members on RSBY card

Coloring variables

- Date RSBY card acquired
- Why household no longer has RSBY card
- Expected RSBY card but did not receive it

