8.2 Utilization

The following were asked separately for a sickness (as screened using the same criteria as our PHES instrument) and the most serious treated case (defined as largest expense or longest length of stay).

- Seek treatment for an illness (with illness defined by PHES screens)
- Visit a clinic
- Visit a hospital
- Visit a private (versus government) hospital
- Length of stay
- Any medical expenses

The following outcomes were measured on all subjects

- Had a day surgery
- Number of day surgeries
- Type of day surgery
- Tried to use RSBY card
- Were able to use RSBY card
- How many times did you visit a hospital?
- How many nights did people stay in a hospital across all hospital visits?
- Knowledge about RSBY (number correct out of 4 questions)
- Subjective willingness-to-pay for RSBY

Coloring variables for last 2 sets of outcome variables

- Did you have an illness (as defined by PHES screens)
- Number of household members on RSBY card
- Age (child or adult) and gender of household members on RSBY card
- Household has BPL card
- When RSBY stopped being valid
- Unable to use RSBY card
- Expected RSBY card but did not receive it
- Why household did not try to use RSBY card

- Why household was unable to use card
- Age (child or adult) and gender of person who was ill (with illness defined by PHES screens)
- Did RSBY card pay for day surgery
- Verified eligibility for NHPS (National Health Protection Scheme or Ayushman Bharat)
- Verified claims under NHPS

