8.5 General coloring variables

The following is a non-exhaustive list of variables that may be used as control variables that measure dosage, specific margins of response or dosage. This list is non-exhaustive as it lists only those variables measured at endline and not otherwise included as a coloring variable above.

- Gender of respondent
- Age of respondent
- Role of respondent in household (relationship to head of household)
- Size of household
- Number of adults in household
- Number of children in household
- Knowledge of BPL households and how many
- Knowledge of BPL households with RSBY cards and how many
- Knowledge of household that successfully used RSBY
- Knowledge about RSBY (number correct out of 4 questions)
- Knowledge of when RSBY scheme expired
- Subjective willingness-to-pay for RSBY
- Knowledge about NHPS
- Does respondent think household is covered by NHPS
- One item test of NHPS (does respondent know about amount of coverage)
- Did any other individuals assist with answering questions during the survey? If so, what is the gender and relationship to respondent? ¹⁷

¹⁷Additional respondents may affect the response quality in both positive and negative ways. For finance questions, these individuals may improve the precision of the responses. For health questions, these individuals may lead to decreased precision. Please note that enumerators were instructed to administer health questions without any additional individuals present to minimize this concern.

9 Structural modeling

We plan to develop an economic model of household financial decisions and health status. We will structurally estimate the model using the experimental variation, to quantitatively reconcile the rich set of empirical results and perform counterfactual analysis.

10 Why is higher price for insurance associated with higher utilization?

At midline we found that individuals in group C, which had to pay a premium for insurance but did not get an unconditional cash transfer, had higher rates of utilization of the RSBY card. We will explore three explanations. First, individuals that value insurance more because they are more likely to use it are more likely to take up insurance, i.e., there is selection. Second, a higher price for a good sends a positive signal about the quality of the good, and higher quality goods are consumed more. Third, there is some sunk cost effect.

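### Section 10.3 predicts lower purchase under price signaling but lists only utilization tests, and Section 10.4 then counts a failure of support as evidence for sunk costs

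*Combined protocol and SAP*

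**What the plan says.** Section 10 asks why a higher price goes with more use of the RSBY card, as seen in group C at midline. At its opening it describes signaling in terms of consumption: "a higher price for a good sends a positive signal about the quality of the good, and higher quality goods are consumed more".

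Section 10.3 turns this into a prediction about peers. Where more villagers got insurance at a lower price, individuals "should perceive insurance as having less value and thus purchase it less themselves". It then introduces two tests of that prediction, both holding the household's own group fixed:

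- Against prices paid by other sample households in the village: "the household should attempt to or utilize care more the higher is price paid by other households".
- Against prices paid more widely in the village, including its below-poverty-line share: "the household should attempt to or utilize care more the higher the price paid by other households that are in the same village".

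Neither names purchase, take-up or perceived value. Both kinds of outcome are listed elsewhere: take-up at the 2015 enrollment in Section 8.1.1, and "Subjective willingness-to-pay for RSBY" in Section 8.2.

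Take-up is used in other places. Of the village-arm Wald test, Section 7.1 says: "This test can be conducted for both take-up and any outcome variable of interest". Section 7.3 uses it for own price ("Hypothesis (2) will be tested by examining how takeup of insurance varies between free and not free"), and Section 10.2 asks who enrolls, given own arm.

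Section 10.4 pre-specifies no test of sunk costs. It treats any failure to support selection or signaling as support for sunk costs.

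**The concern.** The prediction runs from peer price to perceived value to purchase, while the listed tests go straight to use of care. Use across all households in an arm is enrollment multiplied by use per enrollee, so a fall in purchase reaches it only in diluted form.

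A second force may oppose it. Section 11 expects use of the scheme to grow with the number of people already using it. Villages with more free insurance can also have more enrollees, so word of mouth can raise use where signaling should lower it. A flat utilization result could then mean no signaling, or signaling offset by learning. Under Section 10.4 both readings would be entered as evidence for sunk costs, an explanation with no test of its own.

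**Working it through.** No stated figure is in dispute. The steps below set prediction against tests, then ask whether the missing test is feasible.

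**1. Outcome named at each step**

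| Place | Outcome | Contrast |
|---|---|---|
| 10.3, prediction | perceived value, purchase | peer price |
| 10.3, first test | attempted or actual use | price paid by sample peers |
| 10.3, second test | attempted or actual use | price paid across the village |
| 7.1, Wald test | take-up, optional | all village arms jointly, no sign |
| 7.3, hypothesis (2) | take-up | own price |
| 10.2 | enrollment, card retention | baseline sickness or risk aversion |

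No row pairs purchase with peer price and a predicted sign.

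**2. Randomized variation in peer price (Table 1)**

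Check of the Total row for group A: 0.15 × (30 + 30 + 30) + 0.35 × 70 + 0.20 × 10 = 13.5 + 24.5 + 2 = 40, as printed.

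Share free among sample households offered RSBY, A/(A+B+C):
- Arms I and II: 30/90 = 33%
- Arm III: 30/50 = 60%
- Arm IV: 70/90 = 78%
- Arm V: 10/70 = 14%

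**3. Peer coverage moves too**

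Apply the enrollment rates in Section 5.4 (A 78.4%, B 70.4%, C 58.6%, D none) to the sample mix:
- Arm IV: 0.7 × 78.4 + 0.1 × 70.4 + 0.1 × 58.6 = 67.8% enrolled
- Arm V: 0.1 × 78.4 + 0.3 × 70.4 + 0.3 × 58.6 = 46.5% enrolled

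In this contrast the cheaper villages also have more enrollees, which is the condition for word of mouth to oppose signaling.

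**4. Size of an offset (illustration)**

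Take-up in B and C averages (70.4 + 58.6)/2 = 64.5%. If it fell by 6.1 points to 58.4%, use across all B and C households would be unchanged if use per enrollee rose by 64.5/58.4 − 1 = 10.4%.

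**5. Power of a take-up test in B and C, arm IV against arm V**

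Only B and C can show a purchase effect, since A is free and nobody in D enrolled. Assumptions: households split across village arms as villages do, two-sided 5% level, 80% power.

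- Households, arm IV: 11,089 × 0.35 × 0.20 = 776, in 424 × 0.35 = 148 villages, 5.23 per village
- Households, arm V: 11,089 × 0.20 × 0.60 = 1,331, in 424 × 0.20 = 85 villages, 15.69 per village
- Design effect in each arm: DE = 1 + (m − 1) × ICC, where m is households per village
- SE = √[0.645 × 0.355 × (DE₄/776 + DE₅/1,331)]
- Detectable gap = (1.96 + 0.84) × SE

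The plan gives no intracluster correlation (ICC), so a range is assumed:

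| ICC | 0 | 0.02 | 0.05 | 0.10 | 0.20 | 0.30 |
|---|---|---|---|---|---|---|
| Detectable gap (points) | 6.1 | 6.5 | 7.2 | 8.1 | 9.8 | 11.2 |

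**The case against.** The strongest reply is that utilization is the right outcome. Section 10 sets out to explain higher use and describes signaling as raising consumption. An effect on take-up alone would not show that signaling drives use of the card. This stands, and the utilization tests should stay.

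A reader might infer that the purchase prediction is tested nowhere, or that take-up goes unused. The documents do not support either. Section 7.1 permits the village-arm test on take-up, equation (2) applied to the 8.1.1 outcome would estimate how take-up in B and C varies with village composition, and Sections 7.3 and 10.2 use take-up for other questions. What is missing is a named, signed test tied to signaling and to the 10.4 rule.

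A reader might also infer that the utilization tests would usually miss a real effect. In the IV against V comparison, without clustering, suppose a 6.1-point fall in purchase and an assumed 5% to 20% of enrollees using the card. Power on use is then about 7% to 13%, but only if signaling acts through purchase alone. If use per enrollee also fell by 10% to 20%, the range is wide. At 5% use and a 10% fall, 3.2% is compared with 2.6% and power is about 12.5%. At 20% use and a 20% fall, 12.9% is compared with 9.3% and power is about 72%. The plan's own tests also cover all groups and village arms, so this is not their power.

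Take-up has weaknesses of its own:
- Assignment was disclosed and enrollment held in the same May and June 2015 drive, with three weeks to buy, so peer prices may not have spread before purchase.
- The data were in hand when the plan was written, and Section 5.4 reports them by arm and district.
- Endline willingness to pay was to be asked in 2019, after RSBY ended in the state in August 2018, so it reflects later experience.

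These points argue for adding take-up, not for putting it ahead of utilization.

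**Conclusion.** The point holds in a limited form. Within Section 10.3 the stated prediction concerns perceived value and purchase, and both listed tests concern use. This follows from the text and rests on no assumption. It has a consequence because Section 10.4 turns non-support of signaling into support for sunk costs, while use may also be pushed the other way by peer coverage.

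Take-up adds information because purchase largely preceded any use of the card by study peers, so it is less exposed to word of mouth about use. The test is feasible: detectable gaps run from about 6 to 11 points over the assumed intracluster correlations. That range illustrates one contrast between two village arms. That contrast changes the whole mix of arms, not only the free share. The documents do not show how large a signaling effect to expect, so it remains open whether a gap of that size is plausible.

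**What to change.** 1. Add to Section 10.3 a test of 2015 RSBY take-up among arm B and C households by the village share assigned to free RSBY. Use equation (2) with the 8.1.1 outcome, state the predicted sign (lower take-up where more is free), cross-refer to the Section 7.1 take-up test, and keep two-sided p-values as in Section 11.1.
2. Name subjective willingness to pay for RSBY as a supporting outcome.
3. Report both alongside the two utilization tests, and say how Section 7.4 applies now that several outcomes bear on one hypothesis.
4. Amend Section 10.4 so that a utilization null alone does not count as failure of the signaling explanation.
5. State the limits: take-up was collected before the plan was written, peer prices may not have spread fully before purchase, and endline willingness to pay reflects later experience.

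The cost is plan wording and one more regression on outcomes already listed, with no new data. Because the take-up data were already in hand, the added test should be labelled as specified after collection. A take-up null would stay ambiguous on timing, so it should not by itself be credited to sunk costs either.
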